6.4 Visit 1 (2nd week ±2 days)

- (1) Weight measurement;
- (2) Vital signs and physical examination;
- (3) Urine pregnancy test for women of childbearing age with abnormal menstruation;
- (4) Routine blood tests;
- (5) Routine urine tests;
- (6) Biochemical indexes: Liver function, renal function, blood glucose, and blood lipid;
- (7) Coagulation function;
- (8) Record AEs;
- (9) Complications.

6.5 Treatment 2 (4th week ± 2 days)

- (1) Weight measurement;
- (2) Vital signs and physical examination;
- (3) Routine blood tests;
- (4) Routine urine tests;

- (5) Biochemical indexes: Liver function, renal function, blood glucose, and blood lipid;
- (6) Coagulation function;
- (7) Treatment with UC-MSC;
- (8) Record AEs;
- (9) Complications.

6.6 Treatment 3 (8th week ±7 days)

- (1) Weight measurement;
- (2) Vital signs and physical examination; urinary pregnancy test was performed in women of

childbearing age, such as abnormal menstruation.

- (3) Routine blood tests;
- (4) Routine urine tests;
- (5) Biochemical indexes: Liver function, renal function, blood glucose, and blood lipid;
- (6) Coagulation function;
- (7) Treatment with UC-MSC;
- (8) Record AEs;
- (9) Complications.

6.7 Visit 2 (12th week ±7 days)

- (1) Weight measurement;
- (2) Vital signs and physical examination;
- (3) Urine pregnancy test for women of childbearing age with abnormal menstruation;
- (4) Routine blood tests;
- (5) Routine urine tests;
- (6) Biochemical indexes: Liver function, renal function, blood glucose, and blood lipid;
- (7) Coagulation function;
- (8) HBV DNA quantification;
- (9) AFP;
- (10) Upper abdominal ultrasound;
- (11) Record AEs;

(12) Complications.

6.8 Visit 3 (24th week ±14 days)

- (1) Weight measurement;
- (2) Vital signs and physical examination;
- (3) Urine pregnancy test for women of childbearing age with abnormal menstruation;
- (4) Routine blood tests;
- (5) Routine urine tests;
- (6) Biochemical indexes: Liver function, renal function, blood glucose, and blood lipid;
- (7) Coagulation function;
- (8) HBV DNA quantification;
- (9) AFP;
- (10) Upper abdominal ultrasound;
- (11) Record AEs;

(12) Complications.

6.9 Visit 4 (48th week ±14 days)

- (1) Weight measurement;
- (2) Vital signs and physical examination;
- (3) Routine blood tests;
- (4) Routine urine tests;
- (5) Biochemical indexes: Liver function, renal function, blood glucose, and blood lipid;

(6) Coagulation function;

- (7) HBV DNA quantification;
- (8) AFP;
- (9) Upper abdominal ultrasound;
- (10) Record AEs;
- (11) Complications.

6.10 Visit 5 (24 months ±15 days)

(1) Survival status: Telephone call t;

(2) Whether liver cancer occurs or not: Telephone call t.

6.11 Visit 6 (48 months ±15 days)

- (1) Survival status: Telephone call;
- (2) Whether liver cancer occurs or not: Telephone call.

6.12 Visit 7 (60 months ±30 days)

- (1) Survival status: Telephone visit;
- (2) Whether liver cancer occurs or not: Telephone call t.

6.13 Visit 8 (75 months ±30 days)

- (1) Survival status: Telephone call;
- (2) Whether liver cancer occurs or not: Telephone call.

6.14 Unplanned visits (when the study requires it or after withdrawal from the trial ahead of time)

If the subject needs additional visits (such as follow-up monitoring of adverse reactions or AEs) or withdraws from the trial ahead of time, the laboratory and auxiliary examinations should be improved as much as possible, recording AEs and the accompanying treatment. The measures taken by the researchers, including the results of laboratory tests, should be recorded in the original medical records and in the planned out-of-plan visit table in the CRF.

7 Efficacy Assessments

7.1 Survival analysis

The patients will be followed up for 75 months to record their survival status and survival rate after their first UC-MSC infusion. During the follow-up period, the survival rate of those patients is dependent on the survival status at the last visit point after the first infusion. The time of death of those patients will be recorded and the survival rate will be calculated.

7.2 Secondary Efficacy Assessments

Liver function (including the levels of albumin [ALB], prothrombin activity [PTA], total bilirubin [TBIL], and CHE) will be evaluated at 12, 24, and 48 weeks after the first UC-MSC

infusion.

The complications assessment will be followed-up for 48 weeks post-treatment (including infection, gastrointestinal bleeding, encephalopathy, and hepatorenal syndrome).

The diagnosis of complications

The diagnosis of ascites and hepatorenal syndrome will be made according to the AASLD ascites guidelines for liver cirrhosis (2004).

The diagnosis and treatment of hemorrhage and cirrhotic variceal bleeding will be made according to the AASLD guidelines for liver cirrhosis (2008).

The diagnosis of hepatic encephalopathy will be made according to guidelines of the 11th World Congress of Gastroenterology (WCOG), a working group that was established to discuss and summarize hepatic encephalopathy, and "The definition, nomenclature, diagnosis and quantitative analysis of hepatic encephalopathy" was published in the journal of the American society of hepatology in 2002.

8 Concomitant Diseases and Treatments

8.1 Concomitant diseases

If other diseases (excepting HBV infection and related diseases) are found in patients before signing informed consent, they would be considered as comorbid diseases and will be recorded on the CRF.

8.2 Concomitant treatments

Except for infusion of UC-MSC, all other treatments given to subjects at the time of entry into the trial or at any time during the trial will be considered concomitant treatment and the drugs used should be recorded in the CRF under their generic names. The concomitant drugs must be necessary for the subjects to use during the trial. The use of concomitant drugs could be allowed if the researchers consider that those drugs have no influence on UC-MSC efficacy. Meanwhile, the dose of the concomitant drugs should be kept to a minimum.

9 Safety evaluation

It is the responsibility of the researchers to identify and record events that meet the definitions of adverse events (AEs) and serious adverse events (SAEs) specified in this study.

Long-term safety is a major concern for this trial. Hepatocellular carcinoma (HCC) occurrence is defined as the long-term adverse events in this clinical trial. The duration between the first infusion and timepoint of HCC occurrence will be recorded during 75 months of follow-up. This duration will be defined as survival rate of patients without HCC.

9.1 Definition of AEs

An AE is defined as an untoward medical occurrence in a participant in this clinical trial that does not necessarily have a causal relationship with this treatment. Hence, any new unfavorable or unexpected sign (such as an abnormal laboratory finding), symptom, or disease temporally associated with the use of study drug, whether or not considered related to the study drug.

9.2 Definition of SAE

An SAE is any unexpected medical events occurrence that at any dose:

(1) Causes death;

(2) Is life-threatening (defined as an event in which the subject was at risk of death at the time of the event; it does not refer to an event which hypothetically might have caused death if it were more severe);

(3) Results in hospitalization or prolonged hospitalization.

In general, "hospitalization" means that the subject is not suitable for observation or treatment in the outpatient or emergency department, but requires formal admission or emergency observation (at least overnight). A complication that occurs during hospitalization is defined as an AE. If the length of stay in a participant is extended or any symptoms is met other than the SAE standard, it is also defined as SAE. If the patient needs elective surgery for a previous disease and the disease does not progress from the baseline, these conditions do not define an SAE;

(4) Disability, which refers to a person's substantial loss of normal living ability, excluding minor symptoms such as simple headache, nausea, vomiting, diarrhea, influenza, accidental injury, etc. Although these symptoms may have an impact on the ability of daily life, they do not

represent substantial or long-term living ability loss;

(5) Congenital malformations or Congenital anomaly.

Some medical or scientific judgment is needed to determine whether urgent reporting is required in such a situation. Medical event(s) that might not be immediately life-threatening or result in death or hospitalization but, based upon appropriate medical and scientific judgment, might jeopardize the subject or might require medical or surgical intervention to prevent one of the other serious outcomes listed in the definition above, which are defined as important medical events. Examples of such events include invasive or malignant cancer; allergic bronchospasm requiring intensive care in the emergency room or home; hematodyscrasia or convulsions before been hospitalized; and drug dependence or drug abuse.

In this study, the assessment of adverse events (AE) refers to the evaluation of the occurrence and severity of adverse events through medical history, vital signs, physical examination, and laboratory examination within 24 weeks after the first infusion of UC-MSC, which includes serious and important AE evaluation.

9.3 Abnormal clinical test or other abnormal indicators as adverse events or serious adverse events

If the researchers considered that abnormal laboratory tests (such as clinical biochemistry, hematology, urine analysis) were clinically significant, or other abnormal indicators (such as electrocardiogram, vital signs, or physical examination.) were clinically significant and met the definition of an AE or SAE, it would be recorded as an AE or SAE as well as being described by the symptoms and signs of the subjects. It should be regarded as AE or SAE if the clinically significant laboratory abnormalities and other abnormalities were found after the use of UC-MSC, or at the time of baseline assessment and are aggravated after the beginning of the study. However, the results of clinically significant abnormal laboratory tests or other abnormalities associated with the diseases would not be regarded as AE or SAE unless the researchers determined that the condition of the subject became more serious than expected or required medical treatment (such as withdrawal from this clinical trial or medical intervention). If laboratory findings or other anomalies that were present or found at the beginning of the study

are not aggravated, these events would be not included in AE and SAE.

Researchers will determine the clinical significance of an abnormal laboratory examination or other abnormalities according to the US national cancer institute standard and the actual situation of the subjects. All abnormal laboratory test results will be listed by the data statistician after the trail; meanwhile, the severity of those results is evaluated according to the NCI standard.

9.4 AE and SAE Collection and Recording

When an AE or SAE occurs, researchers have a responsibility to review all the relevant records (such as course records, laboratory tests, and diagnostic reports) and to record event-related data in the subjects' CRF.

Researchers should try their best to judge events based on symptoms, signs, or other clinical data. In this case, the diagnosis should be a specific AE or SAE and be recorded as such, not a single signs or symptoms of the subject.

9.5 AE and SAE assessment

9.5.1 Severity determination of an AE

Researchers should assess the severity of each reported AE and SAE based on their clinical knowledge and professional guidelines. The AE recorded in CRF should be classified according to the NCI-CTC AE 4.0 standard (see Appendix 4 for common AE grading standards):

Grade 1. Mild: Patients are asymptomatic or present mild signs; only clinical or diagnosis observation results are obtained; there is no need for interventional therapy;

Grade 2. Moderate: Patients need minimum, local, or non-invasive treatment; the ability of their instrumental daily life activities * is limited;

Grade 3. Serious or clinically significant, but not immediately life-threatening; hospitalization or prolonged hospitalization; disability; limited ability to take care of oneself via daily activities **

Grade 4: The abnormality leads to life-threatening consequences; the need for urgent intervention by clinical therapy;

Grade 5: An AE leads to death.

Illustration: The semicolon used in grade description mentioned above means "or";

A single dash means that this Grade does not exist;

Not all AE contain all levels. Thus, some AEs have less than five Grades to choose from;

Grade 5 (death) does not apply to some AEs, so there is no such level;

Activities of daily living (ADL);

*Instrumental daily life activities include, for example, cooking, shopping, using the telephone, and money management.

** Personal daily activities include, for example, bathing, undressing, eating, washing, taking medicine, and the patients is not bedridden.

9.5.2 The judgment of causality

The researchers should judge the relationship between each AE and SAE and UC-MSC treatment based on their clinical experience. The relationship between an AE and UC-MSC treatment will be evaluated according to five grades: Surely related to, probably related to, might be related to, and surely not related to.

Adverse reactions refer to the sum of the first three grades. Other reasons, such as the natural history of potential diseases, other simultaneous treatments, risk factors, and temporary events related to UC-MSC treatment, need to be considered and examined. Researchers should also consult the handbook of clinical researchers and the UC-MSC treatment-related data for evaluation.

9.6 AE and SAE follow-up

Researchers should collect the records of AEs an SAEs at the beginning of signing informed consent to the completion of follow-up by spontaneous reports or medical examinations. Screening reports or findings of AEs and SAEs should also be reported in writing (including e-mail) by the unit responsible for clinical research and further processed in accordance with the requirements of the Medical Ethics Committee and clinical trial institutions of the center. Once the AE or SAE is reported, the researchers should interview each subject with the AE or SAE and provide the unit responsible for the clinical study with information about the event. All AEs and SAEs recorded that persisted from the previous visit or revisit should be reviewed during current

visit or revisit.

All patients with AEs and SAEs must be visited until their AE or SAE is alleviated, becomes stable, another explanation for the cause of the event is found, or until the patient is lost from follow-up. The AE and SAE part of the CRF should be updated timely when the problem is resolved. The researchers could add additional tests to the visit, which might help to clarify the nature or cause of the AE or SAE. This might include additional laboratory tests or studies, pathological examinations, or consultations with other professionals.

The unit in charge of the clinical research might require the researcher to complete or arrange additional examinations or assessments that could help to clarify the nature or causes of an AE or SAE, and the researcher is obliged to assist. If subjects die during participation in the study or an approved visit period, their autopsy results, including histopathological examination, should be provided to the unit responsible for the clinical study. New or updated data should be recorded on the initially completed CRF SAE page, and the researcher should sign and date the new or updated data. The CRF SAE update page shall be submitted to the unit responsible for clinical research in accordance with the provisions of 9.6.1.

9.6.1 SAE Reporting

As soon as the researchers realize that the subjects have developed an SAE, they have to undertake immediate treatment and report to the unit responsible for the clinical study within 24 hours. The SAE report should be record all available event-related information as completely as possible, be signed by the researcher (or designated person), and submitted to the unit responsible within a specified period of time. Even if the researchers did not obtain all the data on the SAE, they could report to the unit responsible for the clinical study on the relevant pages of the CRF and do not need to wait for other results. The CRF page of SAE can be updated when additional information is available.

In the initial report, the researchers should assess causality based on section 9.5.2 (judgment of causality). Researchers can send the SAE report by fax, which is the best way to submit this information to the person in charge of the research project. Telephone notification might be undertaken and a copy of the SAE report might be sent the next day in the absence of facsimile

equipment. However, telephone notification cannot replace the researchers' completed and signed SAE report.

9.6.2 AEs and SAEs after the study

AEs and SAEs after the study refers to any event that occurs outside the visit period of the AE or SAE specified in 9. 3 (method, frequency, and time of discovery of an AE or SAE). Researchers do not have to take the initiative to explore AE and SAE in subjects who had completed clinical studies and interviews. However, if the researcher is aware of any SAE (including death) at any time after a subject has withdrawn from the study, and the event might be related to the MSC, the researcher should promptly notify the unit responsible for the clinical study.

9.6.3 AE and SAE related to participation in the trial

SAE considered to be related to participation in the study (such as procedures, traumatic examinations, and changes in existing treatment options) should be reported promptly to the unit in charge of the clinical study, both before and after treatment.

10 Withdrawal from the study

10.1 Subjects accomplish the trail

We plan to enroll 250 patients in the trial. Participants will be deemed to have completed the clinical trial if they complete all treatments and visit periods (from the screening period to visit 8) as per the study protocol.

10.2 Subjects withdraw from the trial

Each participant may, at any time of the study, withdraw from the study for any reason (special or non-special) without being unfairly treated. The subjects who withdraw from the study will not be restricted in their treatment and may continue to receive conventional treatment or other appropriate treatment.

The medical examinations in their screening period should be cancelled for the enrolled patients who fail to be screened into the study, and the reasons for failure should be recorded in the completion/termination page.

If the successfully screened participants withdraw from the clinical trial during the study period, the medical examination for these subjects should be completed at the current visit, and the reasons for quitting the study should be recorded in the completion/termination page.

11 Data Management

This scheme only provides general requirements for data management. Data entry and modification: Data entry and management shall be performed by the data manager of the statistical unit, and will be managed by using an electronic database. To ensure the accuracy of the data, two data administrators are required to input and proofread the data independently.

For questions in the CRF, the data administrator should fill out the question-answer form and ask the researcher. The data administrator will modify, confirm, and enter the data according to the researcher's answers, and can issue the question-answer form again if necessary. The data administrator will import the data into the designated database, hand over the data to the statistician for statistical analysis, and the statistical analysis will write the statistical analysis report.

12 Statistical analysis

12.1 Sample size

The median disease-free survival was 60 months in 60% of the patients who received the standard medical treatment, and in 85% of those who received the UC-MSC therapy. Assuming a recruitment period of 40 months and a total follow-up period of over 75 months, with 100 patients in each group, the study would need to have power greater than 80% to detect a significant relative risk reduction, at a two-sided α level of 0.05 (PASS 11.0). Based on the dropout or withdrawal rate, we determined a sample size of 125 patients per group.

12.2 Definition and selection of analysis sets

This study used three data sets: A safety set, a full analysis set, and a per-protocol set.

Safety set (SS): SS refers to the set of all subjects who received at least one UC-MSC infusion and had a post-treatment safety record. The SS will be used for safety analysis and the subjects will be analyzed according to the actual treatment received.

Full analysis set (FAS): FAS refers to the set of all subjects who randomly received at least

one UC-MSC infusion. When the main efficacy indicators are missing, the missing data is not filled in, and will be assigned to the unresponsive set. FAS is the primary analysis set and will be used to report the distribution, demographic data, baseline characteristics, compliance, and efficacy evaluation for all subjects. The subjects will be analyzed in a randomized treatment group.

Per-protocol set (PPS): PPS refers to the set that the subjects coincide with the major inclusion criteria, do not coincide with the major exclusion criteria, complete the treatment regimen, do not take banned medication during the trial, and have no other major program violations. PPS will be used to evaluate primary efficacy.

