12.3.3 Safety Analysis

(1) AEs will be encoded according to MedDRA (International Medical Dictionary). The analysis of an AE will be based on the AE that occurs after UC-MSC treatment (TEAE). TEAE

is defined as an AE that occurs or worsens after UC-MSC treatment. For a TEAE in the treatment group, the TEAE may be related to UC-MSC treatment. An SAE will be analyzed according to the classification of system organs and preferred terms, and the number of occurrences and incidence rate will be calculated;

(2) Descriptive statistics will be used to summarize vital signs and laboratory tests. A shift table will be used to describe changes in normal/abnormal results in the laboratory tests before and after UC-MSC administration. In addition, the number and proportion of subjects will be calculated whose laboratory test are normal before treatment, but abnormal after treatment, or whose laboratory test are abnormal before treatment, but aggravated after treatment.

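### As worded, the safety set and the TEAE definition (12.2, 12.3.3) shut control patients out of the general safety analysis, against the protocol's own two-arm wording, and the AE period is stated three ways

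*Protocol*

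**What the plan says.** Safety is the secondary objective (section 2). The control group receives conventional treatment without UC-MSC (3.1), and 125 patients per group are planned (12.1).

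**Safety set and TEAE**
- 12.2: "SS refers to the set of all subjects who received at least one UC-MSC infusion and had a post-treatment safety record". On its use: "The SS will be used for safety analysis and the subjects will be analyzed according to the actual treatment received".
- 12.3.3: the AE analysis is based on TEAEs, and a TEAE "is defined as an AE that occurs or worsens after UC-MSC treatment". It adds: "For a TEAE in the treatment group, the TEAE may be related to UC-MSC treatment".
- 12.3.3: the shift table describes "changes in normal/abnormal results in the laboratory tests before and after UC-MSC administration".

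**AE period**
- 9.2: AE assessment is "within 24 weeks after the first infusion of UC-MSC, which includes serious and important AE evaluation".
- Table 4 and 6.4 to 6.9: AEs are recorded at weeks 2, 4, 8, 12, 24 and 48.
- 9.6: "Researchers should collect the records of AEs an SAEs at the beginning of signing informed consent to the completion of follow-up". Under 10.1 a patient completes the trial at Visit 8, month 75.
- 9.6.2 refers to 9.3 for the AE period. Section 9.3 deals with abnormal test results and gives no period.

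**The concern.** A control patient treated as assigned fails the first condition of the safety set and cannot have a TEAE. The two definitions exclude controls independently, so repairing one would leave the other in force.

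Section 1 describes decompensated cirrhosis as a disease with ascites, variceal hemorrhage, encephalopathy and high mortality. Serious events are therefore expected without any cell therapy. Rates in infused patients alone cannot be separated from that background. Causality grading by unblinded researchers (3.3, 9.5.2) does not replace the randomised comparison.

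The differing AE periods add a smaller problem. A reader cannot tell whether an event between weeks 24 and 48, or after week 48, counts in the 12.3.3 tables.

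**Working it through.** The protocol gives no figure to reproduce here. The check compares the definitions and then shows what the wording costs.

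**1. Who can enter the safety set.** Inputs: 125 per group (12.1), 1:1 allocation, controls without UC-MSC (3.1). If all are treated as assigned, the 12.2 definition admits up to 125 UC-MSC patients and 0 controls, so 125/250 = 50% of those randomised. With a definition that both arms can meet, it admits up to 125 against 125.

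**2. Whether the rest of the text agrees.**
- 12.2 analyses the safety set by actual treatment, which has no purpose if only one treatment can occur.
- 12.3.3 speaks of a TEAE in the treatment group, which implies TEAEs in another group.
- The FAS in 12.2 carries the same infusion condition, yet its patients are analysed by randomised group and 12.3.4 compares two arms on it.
- For liver function, 12.3.4 does give controls a starting point: routine medical treatment, alongside the first infusion.

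The operative definitions and the surrounding text cannot both stand.

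**3. What has a between-arm comparison.** Under 12.3.4, complications are tested by Chi-squared or Fisher's exact test, and death and HCC events by Kaplan–Meier and Cox methods. Other AEs, other SAEs and the laboratory shifts appear only in 12.3.3, with no comparator.

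**4. What two arms would offer.** The detectable difference at two-sided 0.05 and n = 125 per arm solves

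z_power = [|p1 − p2|·√n − 1.96·√(2·p̄(1−p̄))] / √(p1(1−p1) + p2(1−p2)) ≥ 0.84, where p̄ = (p1 + p2)/2.

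The control rates are assumptions; the protocol gives none.

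| Assumed control rate | UC-MSC rate detectable with 80% power |
|---|---|
| 5% | 15.8% |
| 10% | 23.2% |
| 20% | 35.9% |
| 30% | 47.2% |

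For example, 10% against 23.2% has p̄ = 0.166, and (0.132 × 11.18 − 1.96 × 0.526)/0.518 = 0.86. These are large differences, but the literal safety set supports no comparison at all.

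**5. The AE periods.** 75 months = 75 × 365.25/12/7 = 326 weeks. The shorter periods cover 24/326 = 7% and 48/326 = 15% of that. The 24-week limit keeps 5 of the 6 scheduled AE visits and drops week 48. From month 24 to month 75 only survival and HCC are collected, by telephone (6.10 to 6.13).

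Under a constant event rate, a 24-week window counts 24/48 = half the events of a 48-week window. The proportion of patients affected falls less, because p24 = 1 − √(1 − p48). For assumed 48-week proportions:
- 10%: 1 − √0.9 = 5.1%, or 51% of the 48-week figure;
- 30%: 1 − √0.7 = 16.3%, or 54%;
- 50%: 1 − √0.5 = 29.3%, or 59%.

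**The case against.** **The intent is clear.** The two-arm wording makes it likely that controls were meant to be included. A reader might infer from the literal definitions that the sponsor decided to leave controls out, or, because the FAS shares the phrase, that even the primary comparison has no control arm. The documents do not support either reading, since 12.3.4 names both groups explicitly. What stands is that two explicit definitions conflict with that intent. In an open-label trial, set membership should not be left to interpretation after results are known.

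**Important harms are compared anyway.** A reader might infer that control events enter no analysis and that harm can be neither shown nor excluded. That goes too far: complications, death and HCC are compared in 12.3.4, and section 9 treats HCC as the long-term adverse event. The gap is confined to other AEs, other SAEs and laboratory shifts.

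**The schedule is weak evidence.** Table 4 does not separate the arms for any row, including the infusion row. Its silence alone does not prove that control AEs are collected. It does contain no restriction to one arm, and complications, which are compared between arms, are recorded at the same visits.

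**The AE periods serve different purposes.** This is partly right. Section 9.6 governs collection and reporting, which may run longer than the assessment in 9.2. A reader might also infer that the incidence denominator is undefined. It is not: the denominator is the safety-set count, and the window changes the numerator. The use of week-48 and later events remains unsettled.

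**The SAP may settle it.** The protocol does not leave these definitions open; it states them. An SAP that follows them inherits the conflict.

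**Conclusion.** The point holds as a contradiction in the protocol's wording. Taken literally and with all patients treated as assigned, the general AE, SAE and laboratory analysis has 125 UC-MSC patients and no controls, although the text around it assumes two groups. The between-arm analyses in 12.3.4 cover complications, death and HCC, on an FAS whose definition has the same fault. No comparator is planned for the rest.

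The AE period is a second and lesser inconsistency between 9.2, the schedule and 9.6, with a cross-reference in 9.6.2 that leads nowhere. The 48-week period comes from the visit schedule and not from a sentence in section 9.

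The safety-set count and the comparison of periods rest on the protocol alone. The detectable differences and the effect of window length rest on assumed event rates, and the latter also on a constant rate.

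**What to change.** 1. **Safety set (12.2):** all randomised patients with a safety record after week 0, analysed by treatment received, with at least one infusion counted as UC-MSC and otherwise as control.
2. **TEAE (12.3.3):** an AE that starts or worsens on or after a week-0 start common to both arms. Use the same start for the laboratory shift tables.
3. **Tables:** show AEs, SAEs and laboratory shifts by arm.
4. **FAS (12.2):** replace the infusion condition with one that both arms can meet, and keep analysis by randomised group.
5. **AE period:** state one analysis window in 12.3.3, its length chosen by the sponsor. Reconcile 9.2, the visit schedule with 6.9, and 9.6 with it, and correct the cross-reference in 9.6.2.

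The window should govern the analysis only. Cutting 9.6 back to week 0 through week 48 would remove collection that begins at consent and would clash with 9.6.3, which requires participation-related SAEs to be reported both before and after treatment.

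The cost is wording and one further column in the safety tables. No visit needs to be added.
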